4.0 Study-Wide Number of Subjects

N/A

5.0 Study-Wide Recruitment Methods

N/A

6.0 Multi-Site Research

N/A

7.0 Study Timelines

Participants who take part in Aim 1 will be involved with the study for the length of the focus group (2 days). We anticipate using the first 10 months of the 24-month project to complete Aim 1. Participants who take part in Aim 2 will be involved with the study for the length of pilot RCT (9 months). We plan to begin recruiting for the pilot RCT in month 11 and expect recruitment to take approximately 3 months.

We anticipate that the duration required to enroll all study subjects will be approximately one year and a half.

PROTOCOL TITLE: txt2protect

We anticipate completing the study approximately 4-6 months after the pilot RCT. The funding period for this project is 2 years; however, we suspect that we may need to request a no-cost extension to wrap up the study.

8.0 Study Endpoints

Primary Outcomes – Aim 2

Feasibility. Intervention feasibility will be evaluated by recruitment and retention in the RCT. We will record recruitment and enrollment statistics at every step (e.g., number of clicks on online ads, number who complete the screener, number of eligible participants, number randomized). Retention rates will be computed for each assessment period. An 80% 9-month retention rate will be used to indicate a feasible intervention.

Acceptability. Intervention acceptability will be assessed at the end of Phases 1 and 2 with an adapted version of a scale used in G2G³⁸ and KIU! (an online HIV prevention intervention; R34MH079714, [name] PI).⁴⁹ The scale includes both open- (“What did you like about the program? What could be improved?”) and closed-ended questions (e.g., “I would recommend a program like this to my friends” 1=strongly disagree to 5=strongly agree). Average scores ≥ 4 will be used to indicate an acceptable intervention.

Vaccination Status. A final confirmatory assessment of HPV vaccination status will be conducted at the 9-month follow-up. Participants will be asked whether they received any doses of HPV vaccine (yes/no) since baseline and if yes, the number of doses and where they were received. Vaccination status will be confirmed by consulting the Illinois Comprehensive Automated Immunization Registry (I-CARE). Pharmacies in Illinois are required to report all vaccinations to the registry,⁵⁰ thus any HPV vaccines administered at a local pharmacy over the trial will be documented in I-CARE. Medical chart data will be sought from those participants who report receiving any doses from their primary care physician over the 9-month trial and those doses are not found in I-CARE. Medical chart data will only be sought for those participants who sign the medical release form (see supporting documents).

Vaccination status will be checked in I-CARE at the beginning and end of the trial. Please see supporting documents and below for additional detail.

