1.0 Objectives

Objectives and Aims

The objective of this project is to develop and pilot test a text messaging intervention to increase human papillomavirus (HPV) vaccination in young adult men who self-identify as gay, bisexual, or queer (which for the sake of brevity, will be referred to as MSM throughout this application, although some men will be sexually inexperienced).

Specific Aim 1: Develop, iteratively refine, and pre-test messages using a 5-step formative research procedure. To achieve this aim we will use a well-established formative approach for designing targeted health interventions. The procedure consists of 5 steps: 1) conduct online focus groups, an online survey, and in-depth interviews to inform message content, 2) draft initial messages based on focus group findings and pilot data, 3) refine message content and assess acceptability using content advisory teams, 4) conduct internal alpha testing to ensure software functionality, and 5) beta test the protocol. Intended users of the program (i.e., MSM aged 18-26 years old from the Chicago metro area) will be recruited to assist with this process.

Specific Aim 2: Test the feasibility, acceptability, and preliminary efficacy of the txt2protect (t2p) text messaging intervention in a pilot randomized controlled trial (RCT). To achieve this aim, 460 unvaccinated MSM (ages 18-26) who live in the Chicago metro area will be randomly assigned to the treatment (t2p) or control condition. The treatment condition will receive a culturally appropriate text messaging-based HPV vaccination intervention based on the IMB model, whereas the control condition will receive a text messaging-based sexual health intervention that includes basic facts about HPV vaccination readily accessible online. Primary outcome measures include intervention feasibility (recruitment and retention in the trial), acceptability (satisfaction with the intervention), and preliminary efficacy as determined by initiation (receipt of the first dose) and completion of the 3-dose HPV vaccine series at the end of the 9-month trial. Vaccination status will be verified by participants' medical records and the Illinois Immunization Registry.

Hypotheses

Specific Aim 2: Participants in the t2p condition (vs. control) will report greater acceptability of the intervention and will be significantly more likely to initiate and complete the 3-dose HPV vaccine series by the end of the trial.

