promoting completion of the 3-dose series due to their convenient locations and longer hours of operation.^{30, 31} 5) We will be recruiting participants directly from the community and thus will be able to *extend the reach of the intervention to those individuals who might not normally see a physician.*^{32, 33} Together, these elements reflect a novel approach to promoting HPV vaccination among young MSM.

Preliminary Data

HPV vaccination among young MSM. To inform the proposed project, Drs. [name], [name], and [name] conducted a pilot study to identify barriers and facilitators to HPV vaccine uptake among young MSM.⁸ We recruited a national sample of 336 MSM aged 18-26 to complete an online survey. 21% had received ≥ 1 dose of HPV vaccine. Provider recommendation was the strongest predictor of uptake such that MSM with a recommendation were over 40 times more likely to have been vaccinated. We also observed disparities in uptake, with lower rates among 21-26 year-olds (vs. 18-20), Latinos (vs. Whites), and HIV-negative (vs. HIV-positive) men. Primary barriers to uptake included lack of information about HPV and the vaccine, lack of provider recommendation, and not having disclosed their sexual identify to their provider.

Reducing barriers to HPV vaccination. In previous work (R03CA138069), [name] identified primary barriers to HPV vaccine uptake among young adult women aged 18-26³⁴ and demonstrated that tailoring intervention materials to women's perceived barriers increased their intentions to receive HPV vaccine.³⁵ Intervention materials addressed common barriers to uptake including lack of information about HPV and the vaccine, concerns about side effects and vaccine safety, low perceived need due to not being sexually active or in a committed relationship, disliking shots, and vaccine cost. In the proposed RCT, we will use a *targeted approach*^{36, 37} such that treatment messages will be specifically designed for MSM (e.g., provide tips to address common and unique barriers to HPV vaccine uptake among young MSM).

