Overview. The primary goal of Aim 2 is to pilot test the intervention to establish feasibility, acceptability, and preliminary efficacy. Young MSM in the Chicago metro area will be recruited primarily online as well as from Howard Brown Health Center, and randomly assigned to the treatment or control condition. The intervention will be divided into two phases: During Phase 1 (weeks 1 through 3) participants will receive about 10 messages per day (similar to G2G). During Phase 2 (weeks 4 through 36) message frequency will decrease to monthly messages. The precise number of messages sent per day and delivery schedule may be altered based on feedback from participants in Aim 1. To give participants sufficient time to get vaccinated and because HPV vaccination is currently achieved with 3 doses administered over a 6-month period, participants will be followed for 9 months. Participants will complete assessments at baseline, immediately after Phase 1, and at the end of the 9-month trial (in order to observe all doses). Upon study completion, vaccination status will be verified by participants' medical records and the Illinois Immunization Registry, which tracks pharmacy-delivered vaccines.

Pilot RCT. Participants will be randomized 1:1 to the treatment or control condition using the REDCap (Research Electronic Data Capture) randomization module. Intervention content will be delivered in two phases over a 36-week period. During Phase 1 (weeks 1 through 3), participants will receive about 10 messages daily. During Phase 2 (weeks 4 through 36), message frequency will decrease to monthly messages. To match for attention, message frequency will be equal across the treatment and control conditions. During Phase 2, participants will receive up to three "pop-up" surveys where they will be able to inform us if/when they receive a/each dose of HPV vaccine so messages can be appropriately tailored (e.g., switch from promoting initiation to completion of the 3-dose series). Participants with a primary care provider will be instructed to contact their provider about receiving the vaccine. If their provider does not carry the vaccine, participants will be directed to seek the vaccine at a local pharmacy (e.g., Walgreens, CVS). Uninsured and underinsured participants will be directed to HBHC, a FQHC that provides care on a sliding fee scale.

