Data for the in-depth interviews will be collected in person or by phone. Interviews will take place in the privacy of the PI's ([name]) office and will last approximately 45-60 minutes. Participants will be able to skip any questions they are not comfortable answering.

Surveys will include sensitive questions such as questions about sexual behavior. The benefits to collecting data online include increased self-disclosure compared to interviewer-based data collection; convenience for the participant, as he can decide when to complete it; and increased safety, as he can decide when and where it is best to answer these questions. Participants will also be able to skip any questions that make them uncomfortable.

We are sensitive to how the survey experience can affect the validity of the data. All online surveys will be as brief as possible and configured for easy completion on multiple platforms (e.g., cell phone, tablet, laptop). Based on previous research, we estimate that the Step 1 online survey will take approximately 10-15 minutes, the baseline survey will take approximately 15-20 minutes, the immediate post-test survey (end of Phase 1) will take approximately 25-30 minutes, and the end of trial survey will take about 15-20 minutes. The shorter version of the end of trial survey offered to participants who are difficult to reach and out of window will take about 5 minutes. Pop-up surveys (during Phase 2) will take less than one minute to complete.

HPV vaccination status will be verified via the Illinois Comprehensive Automated Immunization Registry (I-CARE) and participants' medical chart. Vaccination status will be confirmed in I-CARE for all RCT participants both before participants begin receiving messages and at the end of the 9-month trial. Pharmacies in the state of Illinois are required to report all vaccinations to the registry,⁵⁷ thus any HPV vaccines administered to participants at a local pharmacy over the course of the 9-month trial will be documented in I-CARE.

Additionally, medical chart data will be sought from those participants who report receiving any doses of HPV vaccine from their primary care physician over the 9-month

PROTOCOL TITLE: txt2protect

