trial and those doses are not found in I-CARE. The project coordinator will contact these participants at the end of the trial and ask them to complete the medical release form (see supporting documents). Upon receipt of the signed form, the project coordinator will contact the participant's primary care doctor to verify the number and timing of any HPV vaccine doses that were received during the trial. Medical chart data will only be sought for those participants who sign the medical release form.

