11.0 Data and Specimen Management

Analysis Strategy

Intervention feasibility will be computed as outlined above and summarized in a CONSORT map. Acceptability of the intervention will be assessed with descriptive statistics for the closed-ended items and with the same qualitative approach used for the online FG data for the open-ended items. Intervention efficacy will be assessed using an intent-to-treat approach. T-tests and chi-square analyses will be used to compare baseline characteristics of participants in the treatment vs. control condition. Separate chi-square analyses will be conducted for HPV vaccine initiation (receipt of ≥ 1 dose) and completion (receipt of 3 doses) to assess effects of treatment. Secondary analyses will examine potential differences in IMB constructs at the end of Phase 1 by treatment arm and assess whether they mediate effects of t2p on vaccine uptake. Following [name],³⁴ we will also conduct a detailed analysis of barriers to vaccine uptake among participants who did not get vaccinated over the course of the study to inform additional modifications for the large-scale trial.

Power Analysis

Based on previous studies,^{14, 41, 43, 54} we hypothesize that 18-21% of treatment arm participants will receive their 1st dose of HPV vaccine, compared to 6-8% of control arm participants. The comparison of outcomes between arms, with two-sided alpha = 0.05, will have $> 80\%$ power for all scenarios with N=192 per condition. Based on previous

PROTOCOL TITLE: txt2protect

studies with similar samples (G2G, Keep It Up! [KIU!])^{38, 49} and retention rates as high as 85-95% with follow-ups as long as one year, we anticipate an attrition rate of 5-20%. Using the most conservative estimate (20%) we will enroll 230 participants per arm to account for attrition.

Steps to Maintain Data Security and Confidentiality

Participant privacy and data will be carefully protected. Online surveys will be conducted online using a secure web-based application (REDCap).

To maintain privacy in the online focus groups, all participants will be asked to use pseudonyms rather than their real names, and to refrain from mentioning others by name. This will help to ensure openness. If any personal information is inadvertently disclosed, names or other identifying information will be redacted from the focus group transcripts.

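### The chart back-up for the vaccination outcome covers only primary-care doses, although the trial sends uninsured and underinsured men to HBHC

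*Combined protocol and SAP*

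**What the plan says.** Section 1.0 makes initiation and completion primary outcomes and says status will be verified by "medical records and the Illinois Immunization Registry", with no limit on whose records. The overview of Aim 2 in Section 9.0 repeats this.

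The detailed procedure is narrower. I-CARE is consulted for all trial participants at the start and the end. At nine months each man is asked about doses since baseline, including "the number of doses and where they were received". Under Section 8.0, chart data are then sought only from men who "report receiving any doses from their primary care physician over the 9-month trial and those doses are not found in I-CARE", and only with a signed release. Section 9.0 (Sources of Materials) and Section 25.0 give the same restriction. Under Section 9.0 the coordinator contacts the participant's "primary care doctor to verify the number and timing of any HPV vaccine doses that were received during the trial".

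On where men are sent, Section 9.0 says: "Uninsured and underinsured participants will be directed to HBHC, a FQHC that provides care on a sliding fee scale". Section 19.0 confirms HBHC as the referral clinic where these men are to receive the vaccine. On reporting to the registry, Section 9.0 says: "Pharmacies in the state of Illinois are required to report all vaccinations to the registry". No such duty is stated for clinics.

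The analysis in Section 11.0 reads: "Separate chi-square analyses will be conducted for HPV vaccine initiation (receipt of ≥ 1 dose) and completion (receipt of 3 doses". It does not name the source of evidence that makes a dose count.

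**The concern.** A back-up check should cover the places where the trial expects men to be vaccinated. Here it covers one clinic type, the participant's own primary care, and leaves out the clinic to which the trial itself refers men without adequate insurance. A real dose given there, reported by the man and absent from the registry, has no route to verification under the text. If the outcome means verified doses, that man is counted as unvaccinated. Completion is more exposed than initiation, because it needs all three doses while initiation needs only one.

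**Working it through.** The plan gives no figure on this point to reproduce, so the check sets each route to vaccination against the evidence the plan provides for it.

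1. **Primary care provider** (Section 9.0: men who have one are told to contact him or her). Registry search: yes. Reporting duty stated: no. Chart back-up: yes, with a signed release.
2. **Pharmacy** (Section 9.0: used when the provider does not carry the vaccine). Registry search: yes. Reporting duty stated: yes. Chart back-up: none.
3. **HBHC** (Sections 9.0 and 19.0: uninsured and underinsured men). Registry search: yes. Reporting duty stated: no. Chart back-up: none, unless the man regards HBHC as his primary care.

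Section 9.0 lists these as separate routes, so the third is not plainly contained in the first. It is the only one with neither a stated reporting duty nor a chart check. The second still lacks a back-up if a pharmacy dose fails to appear in I-CARE.

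**What size would depend on.** Let *a* be the share of initiators vaccinated at a non-pharmacy clinic that they do not regard as primary care. Let *b* be the share of those men with no dose in I-CARE. If unverified means unvaccinated, and *a* and *b* are the same in both arms, each verified initiation rate is multiplied by (1 − *ab*). The documents give neither *a* nor *b*. The values below are assumptions, applied to the narrowest planned contrast in Section 11.0, 18% against 8%:

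- *b* = 0 (every such dose is in I-CARE): 18.0% against 8.0%, difference 10.0 points.
- *a* = 20%, *b* = 20%: *ab* = 0.20 × 0.20 = 4%. Rates are 18 × 0.96 = 17.3% and 8 × 0.96 = 7.7%, difference 9.6 points.
- *a* = 20%, *b* = 50%: *ab* = 0.20 × 0.50 = 10%. Rates are 18 × 0.90 = 16.2% and 8 × 0.90 = 7.2%, difference 9.0 points.

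The risk ratio is 18/8 = 2.25 in every line. The product *ab* is also the most that a wider chart check could recover, because some of these men would not report the dose or sign a release. No planning rates are given for completion, so it is not computed.

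**The case against.** The affected group is narrow and may be empty. I-CARE is searched for everyone, so HBHC doses are found if HBHC reports there. The documents do not say whether it does. HBHC is a health center offering sliding-fee care, and a man sent there may well name it as his primary care. Section 8.0 points to supporting documents for further detail, and these or the release form may already cover any provider. The unrestricted promise of medical records in Sections 1.0 and 9.0 suggests loose drafting more than a deliberate exclusion. All of this stands and limits the size. It does not change what the three procedural statements tell the coordinator to do.

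A reader might infer that the plan's claim of more than 80% power fails. The documents do not support that. In the weakest planned scenario, 18% against 8% at 192 per arm, power is 83.3%, and about 7% of all initiators would have to go unverified before it fell below 80%. The other three scenarios tolerate much larger losses. Nothing shows that the loss from this rule reaches 7%, and other losses, such as doses never reported, are not due to it.

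A reader might also infer bias between arms, since the treatment messages cover alternative places to be vaccinated. The example given there is a pharmacy, whose doses the plan expects in I-CARE. The HBHC referral is not limited to one arm, and nothing shows that capture would differ.

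The aim in Section 2.0 of reaching "those individuals who might not normally see a physician" adds little: it concerns recruitment from the community, not where doses are given.

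On counting, Sections 1.0, 8.0 and 9.0 already speak of verified or confirmed status. The natural reading is that a verified dose is required, so the silence of Section 11.0 is a missing detail more than a conflict.

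**Conclusion.** The point holds as a mismatch between the verification procedure and the trial's own referral route, on a primary outcome. Followed literally, the plan gives no chart check to a reported dose from HBHC or another clinic outside the man's primary care when I-CARE does not show it, and this can understate verified initiation and completion. The size is unknown. It depends on how many men are vaccinated at such clinics, how completely those clinics report to I-CARE, and whether the men regard them as primary care; the documents give none of these. With equal capture in both arms the absolute difference shrinks and the risk ratio does not change. Neither bias between arms nor a failure of the power statement is shown. The correction is worth making because it is cheap and bears directly on how the outcome is ascertained.

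**What to change.** 1. In Section 8.0, Section 9.0 (Sources of Materials) and Section 25.0, seek records for any reported dose not found in I-CARE, whatever the provider, naming HBHC and pharmacies as included.
2. In Sections 9.0 and 25.0, have the coordinator contact the provider who gave the dose. The nine-month question on place of vaccination already supplies this. Keep the signed release and the end-of-trial timing.
3. As a clarification in Section 11.0, state that the primary outcome is a dose verified in I-CARE or a provider record, and that self-report-only doses are counted as received in a sensitivity analysis.

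The cost is a short amendment, a few more record requests by the existing coordinator, and a change to the release form if it is limited to primary care. HBHC is already a consortium site. Doses that are never reported, or reported without a signed release, would still be missed if they are not in I-CARE.

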9.0 Procedures Involved

Note: Version 2 of this IRB application was associated with a Just-in-Time request from NIH for this project. Since that time, this project was funded and officially began on July 1, 2016. Some of the attachments associated with the approved (Version 2) IRB application are in draft form. We will be sure to submit updated versions of all study-related documents and report any changes regarding study procedures or personnel as appropriate.

Research Design for Aim 1

Overview. The primary goal of Aim 1 is to develop content for the text messaging intervention and conduct initial pre-testing using a 5-step formative approach developed by [name] and Ybarra:³⁸ (1) Conduct 4 online focus groups to inform message content, (2) Draft initial messages based on focus group findings and our pilot data, (3) Further refine message content and assess acceptability using 3 content advisory teams, (4) Conduct internal alpha testing to ensure software functionality, and (5) beta test the protocol.

PROTOCOL TITLE: txt2protect

Step 1: Develop message content. We will conduct online focus groups (FGs) using a password-protected message board to inform message content and delivery preferences. This approach has been used by [name] and colleagues and proven to be a rich source for intervention development by allowing participants to identify barriers and potential solutions and make suggestions on how to frame intervention content.^{38, 47, 48} Relative to traditional in-person FGs, online FGs can accommodate a larger number of participants who can participate throughout the day from any location at their convenience. FG participants will be required to visit the message board 2-3 times per day for 2 days to respond to the moderators' questions and comments from other participants. We will conduct 4 FGs total, 2 with vaccinated and 2 with unvaccinated participants. See Appendix 1 for a sample moderator script.

To complement the online FGs, we will also conduct an online survey and in-depth interviews. Our pilot data for this project focused on a national sample of YMSM. As the current project specifically targets YMSM in the Chicago area, we would like to gain a better understanding of facilitators and barriers to HPV vaccination for our local population. Although these factors will be assessed in the online focus groups, we believe that these additional data collection formats will allow for a richer understanding of men's knowledge, attitudes, and beliefs regarding HPV vaccination than could be supplied in a focus group alone. See Appendix 8 and 9 for the online survey and interview guide.

Step 2: Draft initial messages. Transcripts from the FGs will be imported into Dedoose,⁵¹ a mixed-methods analysis program. Two rounds of constant comparison analysis will be conducted to create and refine the codebook, which will be followed by a thematic content analysis.^{52, 53} Using these themes in conjunction with results from our pilot work,⁸ [name] will draft an initial pool of messages. Treatment condition messages will be written to directly address IMB components, with special emphasis on barriers relevant to each component. Messages will take into account unique socio-cultural and developmental factors relevant to gay, bisexual, and queer men to ensure that content is appealing and culturally appropriate. Control condition messages will include basic facts about HPV vaccination currently available online plus general sexual health content adapted from G2G. Control messages will be largely informational yet, to ensure a blinded control group, will be aligned with what young MSM might expect in a sexual health program. Messages will be reviewed by Drs. [name], [name], and [name] and subjected to further edits and review, as necessary.

Step 3: Refine messages and assess acceptability. We will use content advisory teams (CATs) to further refine the messages. CAT1 and CAT2 will focus on treatment condition messages and CAT3 will focus on control condition messages. CAT members will receive an email link to the list of initial messages hosted on a secure web-based application called REDCap and will be asked to provide feedback on their overall tone, clarity, and appeal, and to identify their favorite and least favorite messages (See Appendix 2 for draft survey). Several days later, CAT members will take part in a 2-day online FG (similar to Step 1) to discuss the messages as a group and provide suggestions for improvement. Feedback from CAT1 will be used to further refine the messages. This process will then be repeated with another team (CAT2). CAT3 will complete this process for control condition messages. See Appendix 3 for a sample FG guide.

Step 4: Test software functionality. We will conduct alpha testing with the study team to ensure that the text messaging software is functioning correctly. In addition, we will verify the enrollment process and randomization procedure, assess message delivery and display, and correct any programming bugs.

PROTOCOL TITLE: txt2protect

Step 5: Beta-test the protocol. To identify opportunities for improving program usability and to ensure functionality we will beta test the protocol. Twenty participants will be recruited for the beta test. Participants will complete a baseline survey and then receive 5-10 messages daily (similar to the number sent in G2G) for 3 weeks (similar to Phase 1 of the pilot RCT described below). At the end of week 1 and 2, participants will receive a brief check-in survey to provide open-ended feedback on the program. After the final week of messages (week 3), participants will complete a final check-in survey plus additional items to assess intervention acceptability and immediate outcomes of interest (e.g., HPV/HPV vaccine knowledge, IMB constructs, intentions to get vaccinated). See Appendix 4 for draft surveys associated with the Beta-test.

Research Design for Aim 2

Overview. The primary goal of Aim 2 is to pilot test the intervention to establish feasibility, acceptability, and preliminary efficacy. Young MSM in the Chicago metro area will be recruited primarily online as well as from Howard Brown Health Center, and randomly assigned to the treatment or control condition. The intervention will be divided into two phases: During Phase 1 (weeks 1 through 3) participants will receive about 10 messages per day (similar to G2G). During Phase 2 (weeks 4 through 36) message frequency will decrease to monthly messages. The precise number of messages sent per day and delivery schedule may be altered based on feedback from participants in Aim 1. To give participants sufficient time to get vaccinated and because HPV vaccination is currently achieved with 3 doses administered over a 6-month period, participants will be followed for 9 months. Participants will complete assessments at baseline, immediately after Phase 1, and at the end of the 9-month trial (in order to observe all doses). Upon study completion, vaccination status will be verified by participants' medical records and the Illinois Immunization Registry, which tracks pharmacy-delivered vaccines.

Pilot RCT. Participants will be randomized 1:1 to the treatment or control condition using the REDCap (Research Electronic Data Capture) randomization module. Intervention content will be delivered in two phases over a 36-week period. During Phase 1 (weeks 1 through 3), participants will receive about 10 messages daily. During Phase 2 (weeks 4 through 36), message frequency will decrease to monthly messages. To match for attention, message frequency will be equal across the treatment and control conditions. During Phase 2, participants will receive up to three "pop-up" surveys where they will be able to inform us if/when they receive a/each dose of HPV vaccine so messages can be appropriately tailored (e.g., switch from promoting initiation to completion of the 3-dose series). Participants with a primary care provider will be instructed to contact their provider about receiving the vaccine. If their provider does not carry the vaccine, participants will be directed to seek the vaccine at a local pharmacy (e.g., Walgreens, CVS). Uninsured and underinsured participants will be directed to HBHC, a FQHC that provides care on a sliding fee scale.

Treatment condition. Phase 1 content will be presented in 3 modules (1 per week), each reflecting a component of the IMB: Module 1 will address **information** about HPV infection and the HPV vaccine. It will also include a "doctor's blog" to capture the important influence providers have in promoting HPV vaccination and to further legitimize the information. Module 2 will address **motivations** to receive HPV vaccine. Content will address attitudes and social norms about HPV vaccination, vulnerability to HPV infection, and vaccination intentions. Module 3 will focus on **behavioral skills** and self-efficacy for initiating and completing the 3-dose series such as scheduling an appointment, talking with their doctor about the vaccine (and possibly their sexual identity), verifying whether their health insurance covers the vaccine, and finding

PROTOCOL TITLE: txt2protect

alternative locations to receive the vaccine (such as a pharmacy) if it is not carried by their physician. Each module will include tips that address potential barriers relevant to each IMB component. Phase 2 “booster” messages will largely reinforce Phase 1 content to foster continued engagement with the program, although some new content will also be introduced. For example, messages will shift to encourage vaccine completion when a participant initiates the series.

Control condition. Phase 1 content will be presented in 3 modules; however, unlike the treatment group, content will be topic-based rather than theory-based and will focus on general sexual health. Module 1 will address basic facts about HIV and STIs, including HPV. Module 2 will address HIV/STI prevention (e.g., condom use) and will include basic facts about HPV vaccination that are currently available online. Module 3 will address healthy relationships. Phase 2 messages will reinforce Phase 1 content to maintain engagement.

Text Messaging and Data Collection Platform. With the exception of screening survey data (which will be collected using Limesurvey for the Beta test and RCT), study data will be collected and managed using REDCap (Research Electronic Data Capture) an electronic data capture system hosted at Northwestern University. REDCap is a secure, web-based application designed to support data capture for research studies. REDCap added the functionality to send SMS and phone surveys in the 6.6.0 release. This functionality is enabled through the cloud-based telephony service provider Twilio (www.twilio.com). In accordance with the defined text-messaging schedule of the pilot RCT, we will use REDCap to send text messages to participants. We will also use REDCap to inform participants about online assessments. Participants will receive the link to the survey via text message. This will provide consistency for participants in that all messages will be coming from one source. We chose REDCap as our platform because it is cost-effective, user friendly, open source, and scalable, features that will be particularly important in future implementation of the t2p intervention.

Assessments. Participants will complete the screener plus three assessments at baseline, end of Phase 1 (end of week 3), and end of Phase 2 (end of the 9-month trial), with participants initially receiving \$10, \$10, and \$30 for each respective survey. Beginning in June 2018, the incentives were increased so that participants received \$15 each at baseline and the end of Phase 1, and \$45 at the end of Phase 2. The study team hopes that the increase in incentives will help with meeting recruitment and enrollment scopes. The changes to the incentive dollar amounts will be updated on all study materials (e.g. online screener, recruitment materials, intervention/control text messages, surveys, etc.).

For participants enrolled with the original payment structure and still active in June 2018, we will make up the difference at their next scheduled payment. For example, if a participant is in Week 2 when the change in payment is instituted, they would receive the new Phase 1 payment (\$15) plus an extra \$5 for baseline (total \$20) after completing the Phase 1 survey. If a participant is in Month 6 when the change is instituted, they would receive the new Phase 2 payment (\$45) plus an extra \$10 (\$5 each) for baseline and Phase 1 (total \$55) after completing the Phase 2 survey.

Participants who are difficult to reach and are out of window for completing their Phase 2 survey will be offered the option to complete a shorter version of the survey. This survey will take approximately 5 minutes to complete and have an emphasis on the primary outcomes of the study. This will be a last resort option, as we want most participants to complete the full Phase 2 survey. Participants will also have the option to complete this shorter survey online on their own or over the phone with the Project Coordinator. Participants who complete the shorter version of the Phase 2 survey will be

PROTOCOL TITLE: txt2protect

paid \$20 instead of the standard \$45 received by participants who complete the full Phase 2 survey.

During Phase 2, participants may also receive up to three “pop-up” surveys, depending on their vaccination status at the end of Phase 1. Participants who complete a pop-up survey within the designated time frame will be eligible for a monthly \$50 e-raffle. Surveys will be brief and configured for easy completion on multiple platforms (cell phone, tablet). Participants will receive special data collection text messages with the link to each survey. Participants who do not respond will receive up to 3 reminders by text and email. See Appendix 5 for draft surveys for the pilot RCT.

Sources of Materials

Participants enrolled in Steps 1 and 3 will take part in an online focus group. Some participants enrolled in Step 1 will take part in an online survey or an in-depth interview. Participants enrolled in Step 3 (CATs) will also complete a survey to provide feedback on the initial messages. Participants enrolled in Step 5 (beta test) will complete assessments at baseline and immediate post-test (3 week follow-up). Participants enrolled in the pilot RCT will complete assessments at baseline, immediately after Phase 1, and at the end of the 9-month trial. RCT participants may also receive up to three “pop-up” surveys during Phase 2.

Data for the focus groups will be collected using a secure online message board that members of our team have used successfully in previous research. All survey data will be collected online through REDCap, a secure, web-based application designed to support data capture for research studies.

